7.3.2. Adverse Events

The verbatim terms as reported in the CRF by Investigators to identify AEs will be coded using MedDRA version 23.0 or higher and summarized by primary SOC and PT.

AE toxicity will be evaluated using the NCI CTCAE version 5.0 (published 27 Nov 2017).

AE causality is determined by the Investigator using the following assessment categories: unrelated or related.

TEAEs are defined as those AEs with onset on or after the first dose of treatment (i.e., study drug). Events reported with a partial onset date (e.g., month and year are reported, but the day is missing) will be considered to be treatment emergent if it cannot be confirmed that the event onset was prior to the first dose of study drug based on the available date entries.

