2.3.1. Risk Assessment

Details of the potential risks and mitigation strategy are provided in [Table 3](#). Further information on ALXN1840 is available in the IB.

Table 3: Potential Risks and Mitigation Strategy

Potential Risk of Clinical Significance	Summary of Data/Rationale for Risk	Mitigation Strategy
ALXN1840		
Anemia	Anemia has been observed in patients with WD, attributed to overtreatment and resultant Cu depletion, see the IB	Monitoring complete blood count Dose modification (Section 6.6) or discontinuation (Section 7)
Dose-dependent elevations in transaminases (ALT and AST)	Generally mild to moderate in severity, asymptomatic and reversible with dose adjustments were reported, usually after 3-6 weeks of treatment. Results obtained from studies of ALXN1840 and ammonium tetrathiomolybdate in patients with WD; see the IB	Regular monitoring of liver function tests Dose modification (Section 6.6) or discontinuation (Section 7)
Low white blood cell count (leukopenia, bone marrow toxicity)	Leukopenia and bone marrow toxicity (myelosuppression) have been observed in patients with WD, attributed to overtreatment and resultant Cu depletion. Results obtained from studies of ALXN1840 and ammonium tetrathiomolybdate in patients with WD; see the IB	Dose modification (Section 6.6) or discontinuation (Section 7)
Study Procedures and Other		
Liver biopsy: bleeding, infection, liver laceration, pneumothorax, gallbladder injury	Overall rate of serious complications is approximately 1% and mortality at 0.2% Pain is most common complication with one quarter of patients experiencing right upper quadrant or shoulder pain, most common serious complication is bleeding with hemodynamic compromise occurring in 0.01% to 0.5% of cases and includes intraperitoneal hemorrhage, hematoma, and/or hemobilia. Additional complications include but are not limited to transient bacteremia, bile peritonitis, organ injury including pneumothorax (Reddy, 1997 ; Seeff, 2010 ; West, 2010 ; Boyum, 2016)	Abdominal ultrasound is required prior to biopsy to confirm adequate visualization of liver and adjacent structures (Section 5.1) Obese patients (BMI >30 kg/m ²) will be excluded from participating in the study (Section 5.1) Restrictions on antiplatelet and anticoagulant medications (Section 5.3.2) Patients must have a PT-INR < 1.5 (Section 5.2)

Potential Risk of Clinical Significance	Summary of Data/Rationale for Risk	Mitigation Strategy

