8.3. Adverse Events and Serious Adverse Events

AEs will be reported to the Investigator or qualified designee by the patient (or, when appropriate, by a caregiver, surrogate, or the patient's legally authorized representative).

The Investigator and any qualified designees are responsible for detecting, documenting, and recording events that meet the definition of an AE or SAE and remain responsible for following up AEs that are serious, considered related to the study drug or study procedures, or that caused the patient to discontinue the study drug (see [Section 7](#)).

Definitions and procedures for recording, evaluating, follow-up, and reporting AEs and SAEs are outlined in [Section 10.3](#).

8.3.1. Time Period and Frequency for Collecting Adverse Event and Serious Adverse Event Information

All AEs will be collected from the signing of the informed consent until the follow-up visit at the time points specified in the SoAs ([Table 1](#) and [Table 2](#)).

All SAEs will be recorded and reported to Alexion or designee within 24 hours, as indicated in [Section 10.3](#). The Investigator will submit any updated SAE data to Alexion within 24 hours of it being available.

Investigators are not obligated to actively seek AEs or SAEs after conclusion of the study participation. However, if the Investigator learns of any SAE, including a death, at any time after a patient has exited the study, and he/she considers the event to be reasonably related to the study drug, the Investigator must promptly notify Alexion Global Drug Safety (GDS).

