
The Investigator will make an assessment of intensity for each AE and SAE reported during the study and assign it to 1 of the following categories from National Cancer Institute CTCAE v5.0, published 27 Nov 2017:
 
 • Grade 1 Mild; asymptomatic or mild symptoms; clinical or diagnostic observations only; intervention not indicated. • Grade 2 Moderate; minimal, local or noninvasive intervention indicated; limiting age appropriate instrumental activities of daily living. • Grade 3 Severe or medically significant but not immediately life-threatening; hospitalization or prolongation of hospitalization indicated; disabling; limiting self-care activities of daily living. • Grade 4 Life-threatening consequences; urgent intervention indicated. • Grade 5 Death related to AE.

Adverse Event and Serious Adverse Event Recording

Increases in the severity of an AE should be documented to allow an assessment of the AE duration at each level of intensity to be evaluated. Adverse events characterized as intermittent require documentation of onset and duration of each episode, if the severity of the intermittent event changes.

Assessment of Causality

- The Investigator is obligated to assess the relationship between the study drug and each occurrence of each AE or SAE. An Investigator causality assessment must be provided for all AEs (both nonserious and serious). This assessment must be recorded in the CRF and on any additional forms, as appropriate. The definitions for the causality assessments are as follows:
 - Not related (unrelated): There is no causal association with study drug
 - Related: There is causal (temporal) association to the study drug. Other conditions (concurrent illness, concurrent medication reaction, or progression/expression of disease state) do not appear to explain the event; the event corresponds with the known pharmaceutical profile; improvement on discontinuation; reappearance on rechallenge.
- The Investigator will use clinical judgment to determine the relationship.
- Alternative causes, such as underlying disease(s), concomitant therapy, and other risk factors, as well as the temporal relationship of the event to study intervention administration will be considered and investigated.
- The Investigator will also consult the IB and/or Product Information, for marketed products, in his/her assessment.

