5.2.1. Adverse Events

AEs are defined in [Section 10.3](#) of the Protocol (dated 27 May 2022). Details on how to define treatment-emergent adverse events (TEAEs) with partial dates and on how to handle missing or partial AE dates are described in [Section 9.4.1](#).

The occurrence of AEs at each visit will be recorded on designated CRF pages. Each AE is to be characterized (i.e., verbatim term) and information will be provided regarding its seriousness, start and stop dates, intensity, outcome, and causal relationship with the study drug. The safety evaluation will include an assessment of all AEs, SAEs, AE intensity, and AE causality. AE intensity will be evaluated using the National Cancer Institute (NCI) Common Terminology Criteria for Adverse Events (CTCAE) version 5.0 (published 27 Nov 2017). AE causality will be

evaluated by Investigators to be either not related or related. AEs will be coded using the Medical Dictionary for Regulatory Activities (MedDRA) version 23.0 or higher and summarized by primary System Organ Class (SOC) and Preferred Term (PT).

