9.4.1. Adverse Events

The analysis of AEs is described in detail in Section [7.3.2](#).

The TEAEs are AEs with onset on or after the first study drug dose. If the start date of an AE is partially or completely missing and the end (stop) date and time of the AE do not indicate that it occurred prior to the first dose, then the determination of treatment-emergent status will be based on the following:

- If the start year is after the year of the first study drug dose, then the AE is treatment-emergent; else,
- If the start year is the same as the year of the first study drug dose and
 - The start month is missing, then the AE is treatment-emergent; else if
 - The start month is present and is the same or after the month of the first study drug dose, then the AE is treatment-emergent; else,
- If the start date is completely missing, then the AE is treatment-emergent.

All other AEs are considered pre-treatment AEs.

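### TEAEs are defined by onset date alone, so an ongoing pre-dose AE that worsens on drug under one record stays out of the TEAE tables, while Week 48 biopsy events enter them with no planned separate display

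*SAP*

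**What the plan says.** The treatment-emergent rule appears twice in the SAP. Section 7.3.2 has "TEAEs are defined as those AEs with onset on or after the first dose of treatment (i.e., study drug", and the derivation in Section 9.4.1 has "The TEAEs are AEs with onset on or after the first study drug dose". Neither has a clause for worsening after dosing. Section 9.4.1 then assigns the remainder: "All other AEs are considered pre-treatment AEs".

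AEs are collected from signing of consent (Protocol 8.3.1 and the Table 1 footnotes), so the collection window includes Screening and the screening biopsy. On changes in grade, Protocol 10.3 (Appendix 3) says "Increases in the severity of an AE should be documented", so that the time spent at each intensity can be assessed. It does not say whether a new record with a new onset date is opened.

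On causality, Protocol 10.3 says "The Investigator is obligated to assess the relationship between the study drug and each occurrence of each AE or SAE". SAP 5.2.1 lists the attributes of each AE, ending with "intensity, outcome, and causal relationship with the study drug", and SAP 7.3.2 allows two categories, unrelated and related. Procedure relatedness is mentioned in Protocol 8.3, where investigators must follow up AEs that are "considered related to the study drug or study procedures". No causality category or table matches that mention.

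On biopsy risk, Protocol 2.3.1 (Table 3) states: "Pain is most common complication with one quarter of patients experiencing right upper quadrant or shoulder pain". It puts serious complications at about 1%.

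**The concern.** Safety is a secondary objective of a single-arm trial. No control group shows how many events the procedures or the disease would produce by themselves, so readers will take the TEAE tables largely at face value. An onset-only rule distorts those tables in two ways.

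First, it can omit on-drug worsening. An AE that starts at Grade 1 during Screening, is ongoing at first dose and reaches Grade 3 on ALXN1840 under one record is classed by its start date. It would be missing from the relationship and toxicity tables. If it became serious or led to stopping study drug, it would also be missing from the summaries of treatment-emergent SAEs and of TEAEs leading to withdrawal of study drug.

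Second, it brings in events caused by the second biopsy. These are legitimately treatment-emergent by timing, but the overall, SOC, PT and SAE tables give no sign of which events follow a biopsy. Pain in the right upper quadrant after a liver biopsy could be read as a hepatic or gastrointestinal effect of the drug. SAP 7.3.2.5 also counts an AE with a missing relationship as related.

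**Working it through.** The plan gives no figure of its own on this point, so there is none to reproduce. The first part is a reading of the text and the second is simple arithmetic.

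**Part 1: path of a pre-dose AE that worsens on drug**

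1. *Onset.* The AE starts between consent and first dose. It is collected (Protocol 8.3.1).
2. *Grade rises after first dose.* Protocol 10.3 requires the increase to be documented so that duration at each intensity can be assessed. Read naturally, that is one AE passing through several grades.
3. *Classification.* Under SAP 7.3.2 and 9.4.1 the onset date precedes first dose, so the AE is pre-treatment.
4. *Tables.* SAP 7.3.2.5 and 7.3.2.6 (relationship, toxicity) count TEAEs only. Pre-treatment AEs receive a SOC/PT summary and a listing (SAP 7.3.2.1 and 7.3.2.2).

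Routes by which worsening is still seen:

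- Exacerbation of a pre-existing condition is itself an AE (Protocol 10.3). Recorded that way, it has a post-dose onset.
- For intermittent AEs, the onset of each episode is recorded when severity changes (Protocol 10.3).
- Laboratory worsening appears in shift tables, CTCAE-grade shifts and worst post-baseline summaries (SAP 7.3.3.1), whatever the TEAE status.

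What is left is the continuous, non-laboratory AE kept under one record. The documents give no basis for estimating how many there will be.

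**Part 2: Week 48 biopsy events**

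Inputs:

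- 24 patients completing and about 28 enrolled (Protocol 9.2)
- Pain rate 0.25 and serious-complication rate 0.01 (Protocol Table 3)
- Second biopsy at Week 48 (Protocol 1.3), long after first dose, so any complication meets the TEAE definition

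| Quantity | Formula | Result |
|---|---|---|
| Expected patients with biopsy pain | 24 × 0.25 | 6 |
| Binomial 95% range | n = 24, p = 0.25 | 2 to 10 |
| At least one patient with pain | 1 − 0.75^24 | 99.9% |
| Share of a Safety Set of 28 | 6 / 28 | about 21% |
| Range of that share | 2/28 to 10/28 | about 7% to 36% |
| Expected serious complications | 24 × 0.01 | 0.24 |
| At least one serious complication | 1 − 0.99^24 | 21.4% |

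If all 28 patients had a second biopsy, which is possible because the Week 48 column of Table 1 also serves as the Early Termination visit, the expected number with pain would be 28 × 0.25 = 7 and the chance of at least one serious complication 1 − 0.99^28 = 24.5%.

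**The case against.** The best defence is that the gap is narrow and little is hidden. Screening lasts at most 28 days. The documents do not say that a grade increase must stay under the original record, and the requirement to assess duration at each intensity would also fit a new dated record for each change. Pre-treatment AEs are summarised and listed. The listings of SAEs, of AEs leading to withdrawal and of deaths are worded for AEs rather than TEAEs. The drug's main named risks (anaemia, transaminase elevation, leukopenia) are laboratory findings, which the shift tables and eDISH plots track against baseline.

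On the biopsy, counting every post-dose event whatever its cause is the inclusive convention. Events judged unrelated to drug fall in the not-related rows, and AE dates and procedures are both recorded. The safety analysis is descriptive and no primary result depends on it.

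Much of this stands, and it rules out two readings that a reader might infer. One is that pre-dose AEs that worsen on drug never count: exacerbations, new episodes and laboratory changes do. The other is that biopsy events cannot be separated: they can be traced by date and preferred term, and the CRF, which is not among the documents, may hold a procedure-causality item. What is missing is a planned separation.

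The defence does not remove the classification problem. Where worsening is kept under one record, the rule as written gives the wrong class, and a listing does not replace a place in the relationship and toxicity tables. The not-related rows mix biopsy events with all other unrelated events, and tracing them from listings is a post hoc exercise.

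**Conclusion.** The point holds in a limited form and is worth correcting. The onset-only rule misclassifies a continuous, non-laboratory AE that starts between consent and first dose and rises in grade on drug under the same record. The number affected cannot be estimated from the documents and may be small.

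For the Week 48 biopsy, about 6 patients (range 2 to 10; about 21% of 28) could have a procedure-caused TEAE. There is also roughly a one-in-five chance of at least one serious biopsy complication among the treatment-emergent SAEs. These figures assume that 24 patients have the second biopsy, that the protocol's rates apply, that every case of pain is reported as an AE, and that the event is tabulated with the Treatment Period. For patients entering the Extension Period, that visit is also Extension Day 1.

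Two further inferences are not supported. The 21% is the share of patients who could have a procedure TEAE. It does not mean the any-TEAE rate rises by 21 points, because patients with another TEAE are already counted. And the expected 28 × 0.25 = 7 patients with pain after the screening biopsy are not a count of missed worsening: nothing in the documents suggests that this pain lasts to first dose and then increases.

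**What to change.** 1. In SAP 7.3.2 and 9.4.1, define a TEAE as an AE with onset, or with an increase in CTCAE grade, on or after the first dose. State how a grade increase in an ongoing AE is recorded. If the date of the increase is incomplete, follow the SAP's existing approach to partial onset dates and count the AE as treatment-emergent unless the change can be shown to precede dosing.
2. From biopsy and AE start dates already collected, derive a flag for AEs starting within a fixed number of days after a biopsy, with that number set before database lock. If the CRF holds a procedure-relationship item, use it alongside the flag.
3. Show flagged events separately in the main TEAE and SAE tables, keeping the overall counts. Give the flagged screening-biopsy events in the pre-treatment AE summary.

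The cost is a few lines of SAP text, one derived variable and a few extra tables. TEAE counts may rise slightly. No new visits, samples or patients are needed.

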7.3.2.1. Overall Summary of Adverse Events

An overall summary of TEAEs will be presented, including the number of events and the number and percentage of patients experiencing AEs. Percentage will be calculated as $n / N \times 100$, where n is the number of patients with events and N is the number of patients in the Safety Analysis Set. The summary will include categories indicating how many events are TEAEs, treatment-emergent SAEs, and treatment-emergent non-SAEs.

A patient-level listing of all TEAEs will be presented. Separate listings will be produced for SAEs, AEs leading to study drug withdrawal, AEs resulting in death, AEs leading to withdrawal from the study, and pre-treatment AEs (PTAEs).

7.3.2.2. Adverse Events and Serious Adverse Events by System Organ Class and Preferred Term

The number of TEAEs and the number and percentage of patients with events will be presented by SOC and PT. Patients are counted once in each SOC and PT. Percentages will be based on the Safety Analysis Set. The SOCs will be listed in descending frequency as will PTs' within each SOC. If needed, PTs will also be ordered alphabetically.

Treatment-emergent SAEs, treatment-emergent non-SAEs, TEAEs leading to withdrawal of study drug, TEAEs leading to death, and PTAEs will be summarized using the same approach.

7.3.2.3. Adverse Events by System Organ Class

The number of TEAEs and the number and percentage of patients with events will be presented by SOC. Patients are counted once in each SOC. Percentages will be based on the Safety Analysis Set.

7.3.2.4. Adverse Events by Preferred Term

The number of TEAEs and the number and percentage of patients with events will be presented by PT. Patients are counted once in each PT. Percentages will be based on the Safety Analysis Set.

7.3.2.5. Adverse Events and Serious Adverse Events by System Organ Class, Preferred Term, and Relationship

The number of TEAEs and the number and percentage of patients with events will be presented by SOC and PT as described in Section 7.3.2.2 by relationship (related and not related). If a patient has > 1 occurrence of an AE, the strongest relationship to study drug will be used in the summary table. If relationship to study drug is missing, the AE will be assumed to be related. A similar analysis will be conducted for treatment-emergent SAEs.

The number of related TEAEs and the number and percentage of patients with related TEAEs will be summarized by SOC and PT, and separately by PT only. The same analyses will be produced for related treatment-emergent SAEs.

Lastly, the number of TEAEs by SOC, PT, and relationship, without taking into account the highest relationship, will be analyzed. A similar analysis will be conducted for treatment-emergent SAEs.

7.3.2.6. Adverse Events and Serious Adverse Events by System Organ Class, Preferred Term, and Toxicity

The number of TEAEs and the number and percentage of patients with events will be presented by SOC, PTs and toxicity (i.e., CTCAE grade). If a patient has > 1 occurrence of an AE, the highest toxicity reported will be used. The number of TEAEs by SOC, PTs and toxicity, without taking into account the highest toxicity, will also be analyzed.

Additionally, a summary of related TEAEs by SOC, PT, and toxicity using the highest toxicity will be presented.

7.3.3. Other Safety

7.3.3.1. Analyses for Laboratory Tests

Protocol-required safety clinical laboratory assessments include tests under Clinical Chemistry, Hematology, Urinalysis, Coagulation, and Other Tests. Actual values and changes from Baseline will be summarized descriptively for patients with available data for each laboratory parameter by analysis visit. Details for Baseline definition and analysis visit window can be referred to in

Appendix 9.4.4. Missing laboratory data will not be imputed. Multiple records may exist for laboratory parameters with the same date and time and when this occurs, the records will be averaged. When multiple records (including averaged records) exist for a same laboratory parameter within the same analysis visit, the record closest to the target date will be used. If there are multiple records with the same distance from the target date, the latest record will be used. A summary for “Last Assessment” will be included for the last available post-baseline result for each patient. A summary of “Worst Post-Baseline” from all post-baseline data will also be included separately for the Treatment Period and for the Extension Period. For categorical test results, actual values will be summarized by analysis visit. All data including that which is only collected at Screening will be included in by-patient data listings. Laboratory measurements will be listed separately by patient, laboratory test, visit and unit.

The Investigator will evaluate any out of normal range laboratory values and make a determination as to whether the observation is not clinically significant (NCS) or clinically significant (CS).

Where applicable, laboratory results will be classified as “low,” “normal,” or “high” with respect to the parameter-specific reference ranges (i.e., below the lower limit of the normal range, within the normal range, or above the upper limit of the normal range). Contingency tables will be presented for each laboratory parameter to summarize the shift from the Baseline category to all analysis visits. In the tables, count and percentage of patients within each shift category will be included.

Laboratory values outside the normal range will also be summarized and assessed for trends indicating a safety signal. Additionally, a summary and a listing of liver enzyme elevation will be presented.

The following laboratory results will also be graded according the NCI CTCAE version 5.0. Contingency tables will be presented for each laboratory parameter to summarize the shift from the Baseline category to all analysis visits. In the tables, count and percentage of patients within each shift category will be included.

- Hematology: Absolute neutrophil count (neutrophil) (NEUT), total leukocytes (Leukocytes) (WBC), hemoglobin (HGB) (only do the grading for Anemia, no grading for Hemoglobin increased), platelet count (PLAT), Lymphocyte (LYM)
- Coagulation: International normalized ratio (INR)
- Chemistry: Alanine aminotransferase (ALT), albumin (ALB), alkaline phosphatase (ALP), aspartate transaminase (AST), total bilirubin (BILI), creatinine (CREAT), gamma-glutamyl transferase (GGT), glucose (GLUC) (only do the grading the Hypoglycemia, no grading for Hyperglycemia), creatine kinase (CK)

